### 15.0 RESEARCH PARTICIPANT REGISTRATION AND RANDOMIZATION PROCEDURES

#### 15.1 Research Participant Registration

Confirm eligibility as defined in the section entitled Criteria for Patient/Subject Eligibility.

*IRB  
PB*

Amended: 3/5/14

## Memorial Sloan-Kettering Cancer Center IRB Protocol

**IRB#: 07-029A(6)**

Obtain informed consent, by following procedures defined in section entitled Informed Consent Procedures.

During the registration process registering individuals will be required to complete a protocol specific Eligibility Checklist.

All participants must be registered through the Protocol Participant Registration (PPR) Office at Memorial Sloan-Kettering Cancer Center. PPR is available Monday through Friday from 8:30am – 5:30pm at [contact]. The PPR fax numbers are [contact] and [contact]. Registrations can be phoned in or faxed. The completed signature page of the written consent/verbal script and a completed Eligibility Checklist must be faxed to PPR.

### **15.2 For Participating Sites:**

Central registration for this study will take place at Memorial Sloan Kettering Cancer Center.

To complete registration and enroll a participant from another institution, the study staff at that site must contact the designated research staff at MSKCC to notify him/her of the participant registration. The site staff then needs to fax registration/eligibility documents to the **Department of Surgery, Gynecology Service** at MSKCC at **[contact]**.

The following documents must be sent for each enrollment **within 24 hours** of the informed consent form being signed:

- The completed MSKCC eligibility checklist
- The signed informed consent and signed HIPAA Authorization form (Research Authorization)
- Supporting source documentation for eligibility questions (pathology reports, MD notes, physical exam sheets, medical history, prior treatment records).

Upon receipt, the research staff at Memorial Sloan Kettering Cancer Center will conduct an interim review to confirm all documents are received to complete registration.

If the participant meets all criteria, all source documentation is received, the participating site local IRB has granted approval for the protocol, and the site is in good standing with MSKCC, the MSK RSA will send the completed registration documents to the MSKCC Protocol Participant Registration (PPR) Office to be enrolled as stated in section 15.1. The participant will be registered.

### **15.3 Protocol Participant Number at Participating sites**

Once eligibility has been established and the participant is registered, the participant will be assigned an MSKCC clinical research database (CRDB) number (protocol participant

**IRB  
PB**

**Amended: 3/5/14**

## Memorial Sloan-Kettering Cancer Center IRB Protocol

**IRB#: 07-029A(6)**

number). This number is unique to the participant and must be written on all data and correspondence for the participant. This protocol participant number will be relayed back to study staff at the registering site via e-mail and will serve as the enrollment confirmation.

### **16.0 DATA MANAGEMENT REQUIREMENTS FOR PARTICIPATING SITES**

A Research Study Assistant (RSA) will be assigned to the study. The responsibilities of the RSA include project compliance, data collection, abstraction and entry, data reporting, regulatory monitoring, problem resolution and prioritization, and coordinate the activities of the protocol study team. The data collected for this study will be entered into a secure database. Source documentation will be available to support the computerized patient record.

#### **16.1.0 Data and Source Documentation**

##### **Data**

Standardized Case Report Forms (CRFs), directions for use and sign off requirements have been generated for this study. Blank case report forms will be sent to the study staff at each participating site for use. The participating Site PI is responsible for ensuring these forms are completed accurately, legibly and in a timely manner.

##### **Source Documentation**

Source documentation refers to original records of observations, clinical findings and evaluations that are subsequently recorded as data into CRFs. Relevant source documentation to be submitted throughout the study includes:

- MD office visit notes
- Pathology reports
- Photographs
- Clinical assessment forms
- Grade 3-5 toxicities/adverse events not previously submitted with SAE Reports

#### **16.1.1 Data and Source Documentation Submission**

Participating sites should fax the CRFs to MSKCC to the contact provided below. Submissions should include a cover page listing all CRFs enclosed per participant.

**[contact] to the attention of Protocol 07-029 RSA**

#### **16.1.2 Data and Source Documentation Submission Timelines**

- CRFs and source documentation to support data in the CRFs should be submitted according to chart below.

**IRB  
PB**

**Amended: 3/5/14**

## Memorial Sloan-Kettering Cancer Center IRB Protocol

**IRB#: 07-029A(6)**

- Participating sites should respond to data queries within 14 days of receipt.

### 16.2 Data and Safety Monitoring

The Data and Safety Monitoring (DSM) plans at Memorial Sloan-Kettering Cancer Center were approved by the National Cancer Institute in September 2001. The plans address the new policies set forth by the NCI in the document entitled "Policy of the National Cancer Institute for Data and Safety Monitoring of Clinical Trials" which can be found at:

<http://cancertrials.nci.nih.gov/researchers/dsm/index.html>

The DSM Plans at MSKCC were established and are monitored by the Office of Clinical Research. The MSKCC Data and Safety Monitoring Plans can be found on the MSKCC Intranet at: <http://mskweb2.mskcc.org/irb/index.htm>

There are several different mechanisms by which clinical trials are monitored for data, safety and quality. There are institutional processes in place for quality assurance (e.g., protocol monitoring, compliance and data verification audits, therapeutic response, and staff education on clinical research QA) and departmental procedures for quality control, plus there are two institutional committees that are responsible for monitoring the activities of our clinical trials programs. The committees: Data and Safety Monitoring Committee (DSMC) for Phase I and II clinical trials, and the Data and Safety Monitoring Board (DSMB) for Phase III clinical trials, report to the Center's Research Council and Institutional Review Board.

During the protocol development and review process, each protocol will be assessed for its level of risk and degree of monitoring required. Every type of protocol (e.g., NIH sponsored, in-house sponsored, industrial sponsored, NCI cooperative group, etc.) Will be addressed and the monitoring procedures will be established at the time of protocol activation.

### 16.3 Regulatory Documentation

Prior to implementing this protocol at MSKCC, the protocol, informed consent form, HIPAA authorization and any other information pertaining to participants must be approved by the MSKCC IRB/PB. Prior to implementing this protocol at the participating centers, approval must be obtained from the participating center's Local IRB of Record.

The following documents must be provided to MSKCC before the participating site can be initiated and begin enrolling participants:

- Participating site IRB of approval(s) for the protocol, appendices, informed consent form and HIPAA authorization
- Participating site IRB approved consent form
- Participating site IRB's membership list
- Participating site IRB's of Record's Federal Wide Assurance number and OHRP Registration number
- Curriculum vitae and medical license for each investigator and consenting professional

**IRB  
PB**

**Amended: 3/5/14**

## Memorial Sloan-Kettering Cancer Center IRB Protocol

**IRB#: 07-029A(6)**

- Documentation of Human Subject Research Certification and HIPAA training for investigators and key staff members

### 16.3.1 Amendments

Each change to the protocol must be organized and documented by MSKCC and first approved by the MSKCC IRB/PB. After approval at the lead institution, MSKCC will distribute the non-expedited amendments to the participating centers, for approval by their local IRBs.

Participating sites must obtain approval for all non-expedited amendments from their local IRB of record within 90 calendar days of receipt from the MSKCC. If the amendment is the result of a safety issue or makes eligibility criteria more restrictive, sites will not be permitted to continuing enrolling new participants until local IRB approval has been granted.

The following documents must be provided to MSKCC for each amendment within the stated timelines:

- Participating site IRB approval
- Participating site IRB approved, revised documents including the protocol, informed consent form and HIPAA authorization

### 16.3.2 Additional IRB Correspondence

#### **Annual re-approval or Continuing Review Approval**

Annual re-approval from the participating center's Local IRB of Record and the most current approved version of the consent form should be submitted to MSKCC within 7 days of expiration. Failure to submit the re-approval will result in suspension of accrual privileges.

#### **Deviations and Violations**

A protocol deviation on this study is defined as a request to treat a research participant who does not meet all the eligibility criteria, pretreatment evaluation, or who requires alteration in their study plan. If a deviation from the protocol is proposed for a potential or existing participant at a participating site, approval from the MSKCC IRB/PB is required prior to the action. Participating sites should contact the MSKCC PI who will in turn seek approval from the MSKCC IRB/PB

A protocol violation is anything that occurs with a participant, which deviated from the protocol without prior approval from the MSKCC IRB/PB. For protocol violations that are reported after they occur, the participating site should report to MSKCC as soon as possible. The MSKCC PI will in turn report the violation to the MSKCC IRB/PB.

Participating sites should report deviations and violations to the Local IRB of Record as soon

**IRB  
PB**

**Amended: 3/5/14**

## Memorial Sloan-Kettering Cancer Center IRB Protocol

**IRB#: 07-029A(6)**

as possible per local guidelines. Approvals/acknowledgments from the Local IRB of Record for protocol deviations and violations should be submitted to MSKCC as received.

### Other correspondence

Participating sites should submit other correspondence to their local IRB of Record according to local guidelines, and submit copies of that correspondence to MSKCC.

#### 16.3.3 Document maintenance

The MKSCC PI and the Participating Site PI will maintain adequate and accurate records to enable the implementation of the protocol to be fully documented and the data to be subsequently verified.

The participating sites will ensure that all local IRB correspondence (IRB approval letters referencing protocol version date and amendment number, IRB approved protocol, appendices, consent forms, deviations, violations, and approval of annual reviews) is sent to MSKCC and maintained in the regulatory binder on site.

A regulatory binder for each site will also be maintained at MSKCC; this binder may be paper or electronic.

After study closure, the investigator will maintain all source documents, study related documents and CRFs for 3 years.

### 16.4 Quality Assurance

Study personnel will generate monthly registration reports to monitor patient accrual and completeness of registration data. Routine data quality reports will be generated to assess missing data and inconsistencies. Accrual rates, extent and accuracy of evaluations and follow-up will be monitored periodically throughout the study period and potential problems will be brought to the attention of the study team for discussion and action.

Data quality and protocol compliance audits will be conducted by the study team on a regular basis throughout the study period.

#### 16.4.1 Quality Assurance for Participating sites

Each site participating in the accrual of participants to this protocol will be audited by the staff of the MSKCC study team for protocol and regulatory compliance, data verification and source documentation. Audits may be accomplished in one of two ways: (1) selected participant records can be audited on-site at participating sites or (2) source documents for selected participants will be sent to MSKCC for audit. Audits will usually be determined by participant

**IRB  
PB**

**Amended: 3/5/14**

## Memorial Sloan-Kettering Cancer Center IRB Protocol

**IRB#: 07-029A(6)**

accrual numbers and rate of accrual, but can also be prompted by reported SAEs or request of MSKCC PI.

Audits will be conducted at least once shortly after initiation of participant recruitment at a site, during the study (if the trial lasts 3 or more years) and at the end or closeout of the trial at a site. At a minimum, audits will be conducted once a year or more frequently, if indicated. The number of participants audited will be determined by available time and the complexity of the protocol.

The audit will include a review of source documentation to evaluate compliance for:

- Informed Consent documents and procedures
- Adherence to eligibility criteria
- Protocol defined treatment
- Required baseline, on study and follow-up protocol testing
- IRB documents (submitted amendments, annual continuing review reports, SAEs)
- Required specimen submission
- Pharmacy review, if applicable
- Case Report Form submissions to MSKCC: timing and accuracy

A wrap-up session will be conducted at the outside site and preliminary findings will be discussed with the outside site PI and research team. The preliminary results will be sent to the MSKCC PI.

Each audit will be summarized and a final report will be sent to the PI at the audited participating institution within 30 days of the audit. The report will include a summary of findings, participant by participant case review, specific recommendations on any performance and/or shortcomings and request for corrective action, when necessary. When corrective action is required, the participating institution must reply within 45 days of receipt of audit report with their corrective action plan.

A copy of the audit report and corrective action plan (if applicable) submitted by the outside site must be sent to the MSKCC IRB, CRQA and maintained in the department's protocol regulatory binder.

### 16.4.2 Response Review

Since therapeutic efficacy is a stated primary objective, all sites participant's responses are subject to review by MSKCC's Therapeutic Response Review Committee (TRRC). Radiology, additional lab reports and possibly bone marrow biopsies and/or aspirates will need to be

**IRB  
PB**

**Amended: 3/5/14**

## Memorial Sloan-Kettering Cancer Center IRB Protocol

**IRB#: 07-029A(6)**

obtained from the outside sites for MSKCC TRRC review and confirmation of response assessment. These materials must be sent to MSKCC within sixty days of request to the site.

### 16.5 Noncompliance

If a participating site is noncompliant with the data and regulatory requirements set forth in protocol document, accrual privileges may be suspended and/or contract payments maybe withheld (if applicable), until the outstanding issues have been resolved.

## 17.0 PROTECTION OF HUMAN SUBJECTS

**Risks:** It is unlikely that significant risks will be associated with the limited topical use of imiquimod planned in this study.

**Benefits:** Patients with a good clinical response to imiquimod may benefit from future broader application of this therapy.

**Possible Toxicities and Side Effects:** Local application site reactions can be anticipated. Previously reported toxicities/side effects of topical imiquimod are elaborated in section 11.0 of this protocol. While there is no data to suggest the carcinogenicity of topical imiquimod in this setting, the possibility of progression of a lesion to cancer cannot be ruled out.

**Consent Process:** Participation in this protocol is voluntary. All patients will be required to sign a statement of informed consent, which must conform to MSKCC IRB guidelines.

**Costs:** Patients will not be charged for protocol related costs.

**Alternatives:** There are no proven nonsurgical treatments for EMPD. All study patients will be offered surgical treatment for EMPD.

### 17.1 Privacy

MSKCC's Privacy Office may allow the use and disclosure of protected health information pursuant to a completed and signed Research Authorization form. The use and disclosure of protected health information will be limited to the individuals described in the Research Authorization form. A Research Authorization form must be completed by the Principal Investigator and approved by the IRB and Privacy Board.

### 17.2 Serious Adverse Event (SAE) Reporting

Any SAE must be reported to the IRB/PB as soon as possible but no later than 5 calendar days. The IRB/PB requires a Clinical Research Database (CRDB) SAE report be submitted electronically to the SAE Office at [[contact]](mailto:[contact]). The report should contain the following information:Fields populated from the CRDB:

- Subject's name (generate the report with only initials if it will be sent outside of MSKCC)

**IRB  
PB**

**Amended: 3/5/14**

## Memorial Sloan-Kettering Cancer Center IRB Protocol

**IRB#: 07-029A(6)**

- Medical record number
- Disease/histology (if applicable)
- Protocol number and title

### Data needing to be entered:

- The date the adverse event occurred
- The adverse event
- Relationship of the adverse event to the treatment (drug, device, or intervention)
- If the AE was expected
- The severity of the AE
- The intervention
- Detailed text that includes the following information:
  - A explanation of how the AE was handled
  - A description of the subject's condition
  - Indication if the subject remains on the study
  - If an amendment will need to be made to the protocol and/or consent form

The PI's signature and the date it was signed are required on the completed report.

### **17.2.1 Serious Adverse Event (SAE) Reporting for Participating Sites**

#### Responsibility of participating sites:

- Participating sites are responsible for reporting all SAEs to the MSKCC PI via fax or e-mail within 3 calendar days of learning of the event.
- Participating sites should notify the MSKCC PI of any grade 5 events immediately.
- Participating sites should use the SAE Report Template (*appendix #2*) to report SAEs to MSKCC.

#### Responsibility of MSKCC

*IRB  
PB*

Amended: 3/5/14

## Memorial Sloan-Kettering Cancer Center IRB Protocol

**IRB#: 07-029A(6)**

- The MSKCC RSA is responsible for submitting all SAEs to the MSKCC IRB as specified in 17.2.
- The MSKCC PI is responsible for informing all participating sites about unexpected SAEs within 30 days of receiving the stamped SAE from the MSKCC IRB/PB.
- Any report pertaining to a grade 5 event will be distributed to the participating sites as soon as possible.

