### 7.0 RECRUITMENT PLAN (WITH LIMITED WAIVER OF AUTHORIZATION)

As a multi-center trial, participants will be recruited from MSKCC as well as the participating site OSUMC. Potential research subjects will be identified by a member of the patient's treatment team, the protocol investigator, or the research team at each respective institution. If the investigator is a member of the treatment team, s/he will screen their patient's medical records for suitable research study participants and discuss the study and their potential for enrolling in the research study. Potential subjects contacted by their treating physician will be referred to the investigator/research staff of the study.

The principal investigator may also screen the medical records of patients with whom they do not have a treatment relationship for the limited purpose of identifying patients who would be eligible to enroll in the study and to record appropriate contact information in order to approach these patients regarding the possibility of enrolling in the study.

During the initial conversation between the investigator/research staff and the patient, the patient may be asked to provide certain health information that is necessary to the recruitment and enrollment process. The investigator/research staff may also review portions of their medical records in order to further assess eligibility. They will use the information provided by the patient and/or medical record to confirm that the patient is eligible and to contact the patient regarding study enrollment. If the patient turns out to be ineligible for the research study, the research staff will destroy all information collected on the patient during the initial conversation and medical records review, except for any information that must be maintained for screening log purposes. If the woman agrees to study participation, a consenting individual (listed below in section 15.1) will obtain informed consent from the patient until a goal of 20 eligible patients are entered into the study.

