### 9.0 TREATMENT/INTERVENTION PLAN

The patient will be seen in clinic every six weeks during treatment for examination, teaching, and to assess compliance. Imiquimod cream is to be applied 3 times per week for 12 weeks. It should be applied prior to normal sleeping hours, and left on the skin for 6-10 hours. Following the treatment period cream should be removed by washing the treated area with mild soap and water. Examples of 3 times per week application schedules are: Monday, Wednesday, Friday; or Tuesday, Thursday, Saturday application prior to sleeping hours. The technique for proper dose administration should be demonstrated by the prescriber to maximize the benefit of imiquimod therapy. Handwashing is recommended before and after applying imiquimod 5% cream.

Punch biopsy and photography will be performed at the baseline and 12 week time points. If the lesion is still present after 12 weeks of therapy, the treating physician will recommend excision of the lesion four weeks after completion of therapy (week 16). If no lesion is present or the patient refuses surgical excision at week 16, the patient will return for follow-up exams every 3 months for at least 2 years. The treating physician will continue to offer surgical excision at any later point during follow-up if the lesion is still present.

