### 17.3 Safety Reports

- MSKCC will distribute outside safety reports to the participating sites immediately upon receipt.
- MSKCC must submit outside safety reports to the MSKCC IRB/PB according to institutional guidelines.
- Participating sites must submit safety reports to their institution's IRBs within 30 days of receipt from MSKCC or per participating site guidelines.

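### For unexpected SAEs below grade 5, Section 17.2.1 allows up to 35 days before the participating site is told, even with instantaneous IRB stamping, while outside safety reports go out at once

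*Combined protocol and SAP*

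**What the plan says.** The trial has two sites: "participants will be recruited from MSKCC as well as the participating site OSUMC" (Section 7.0). Four rules govern how a serious event becomes known across them.

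- Section 17.2, to the board: "Any SAE must be reported to the IRB/PB as soon as possible but no later than 5 calendar days".
- Section 17.2.1, from the participating site to the lead centre: "Participating sites are responsible for reporting all SAEs to the MSKCC PI via fax or e-mail within 3 calendar days of learning of the event".
- Section 17.2.1, from the lead centre to the participating site: the MSKCC principal investigator is responsible for "informing all participating sites about unexpected SAEs within 30 days of receiving the stamped SAE from the MSKCC IRB/PB". The next bullet makes an exception: "Any report pertaining to a grade 5 event will be distributed to the participating sites as soon as possible".
- Section 17.3, for reports from outside the trial: "MSKCC will distribute outside safety reports to the participating sites immediately upon receipt".

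The treatment against which these times should be read is in Section 9.0: "Imiquimod cream is to be applied 3 times per week for 12 weeks".

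**The concern.** Section 3.1 states that imiquimod has not been studied prospectively in this disease. An unexpected serious event in the trial itself, in the same population on the same regimen, is therefore about the most relevant new safety information a participating investigator could receive. Below grade 5, it has a slower permitted route than a report from outside the trial. The routes between the two sites are also unequal, since the participating site has 3 calendar days to tell MSKCC. The 30-day clock depends on an administrative step, "receiving the stamped SAE from the MSKCC IRB/PB", and not on the event or on its submission to the board.

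Treatment is short, and the only scheduled visit between baseline and the end of treatment is at week 6. A patient at the participating site could use a large part of the course before the local investigator hears of the event. A new patient could also be counselled without that information, although Section 18.0 requires the risks to be explained before inclusion.

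**Working it through.** The plan states no figure for this delay, so there is nothing to reproduce. The check is arithmetic on the time limits.

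**Inputs**
- Course (Section 9.0): 12 weeks × 7 = 84 days; 12 × 3 = 36 applications.
- Event to IRB/PB (Section 17.2): at most 5 calendar days. The section does not say when the count starts; I assume it starts when MSKCC learns of the event.
- Submission to receipt of the stamped report: not given. I show 0, 7, 14 and 30 days as assumptions.
- Receipt of the stamped report to notice at the site (Section 17.2.1): at most 30 days.
- Patients from the participating site (Section 14.0): 1 to 2 a year.
- Week 6 visit window (Section 10.0): days 35 to 49.

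**The 30-day step alone**
30 / 84 = 35.7% of the course; (30 / 7) × 3 = 12.9, or about 13 applications.

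**Longest permitted delay for an event at MSKCC**
Maximum delay = 5 + stamping time + 30.

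| Assumed stamping time (days) | Maximum delay (days) | Share of 84 days |
|---|---|---|
| 0 | 35 | 41.7% |
| 7 | 42 | 50% |
| 14 | 49 | 58% |
| 30 | 65 | 77% |

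With no stamping time, 35 days is 5 weeks, and 5 × 3 = 15 of 36 applications. Each further week adds 3.

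**Against the visit schedule**
Take a patient at the participating site who starts on the day of the event. With no stamping time, notice falls due on day 35, when the week 6 window opens. With 14 days for stamping it falls due on day 49, when the window closes. The whole week 6 visit could then take place uninformed, and the next scheduled visit is at week 12.

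**Exposure**
Patients on treatment at one time = annual number × 84 / 365. This gives 1 × 84 / 365 = 0.23 and 2 × 84 / 365 = 0.46. These are upper figures. Section 14.0 sets the 1 to 2 beside about 7 diagnosed a year at MSKCC, a total of 8 to 9, yet expects only 5 to 8 accruals a year. Not every available patient is expected to enrol.

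**Direction**
An event at OSUMC reaches the MSKCC principal investigator within 3 calendar days, and an event at MSKCC is already known there. The long route therefore matters mainly for OSUMC patients when the event arises at MSKCC.

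**With notice at submission**
The longest permitted delay becomes 5 days: 5 / 84 = 6.0%, and (5 / 7) × 3 = 2.1, or about 2 applications. It no longer depends on the stamping time.

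**The case against.** The strongest reply is that this is a procedural choice with very little exposed to it. Sections 17.2.1 and 17.3 cover different kinds of report, so a reader who infers that they contradict each other goes too far. Waiting for the stamped report is a defensible order of events, and the most severe grade is already expedited. The drug is marketed and Section 11.0 lists many reactions, which narrows what would count as unexpected. Harm would need an unexpected SAE below grade 5 at MSKCC to coincide with a patient on treatment, or about to start, at OSUMC. Nothing here affects the response rate or its precision. All of that stands and keeps the point minor.

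The protocol also gives some protection elsewhere. The SAE report described in Section 17.2 must say whether the protocol or consent form needs amending. Under Section 16.3.1, a safety amendment stops new enrolment at a site until its local board approves. This answers part of the worry about new patients. It acts only once an amendment is issued, and it does nothing for patients already on treatment.

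A reader might infer that 35 days is a minimum or scheduled delay. The documents do not support that. The 5 and 30 days are both ceilings, and same-day notice would comply. Nor does the finding extend to every unexpected SAE, because grade 5 reports are excepted.

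**Conclusion.** The point holds as a minor one. For unexpected SAEs below grade 5, the text permits up to 35 days before the participating site is told if stamping is instantaneous, and longer otherwise, with no upper limit in the documents. That is 42% of the course. It is a permitted maximum; actual practice may be much faster. The clock runs from receipt of the stamped report by the principal investigator and not from the stamp itself, so any transit time adds to the delay. Nothing in the available text shortens the limit for these events.

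The result assumes that the 5-day count starts when MSKCC learns of the event. The figure of at most about 0.2 to 0.5 patients on treatment at OSUMC also assumes that all of the 1 to 2 patients a year enrol.

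**What to change.** Amend the MSKCC responsibilities in Section 17.2.1 so that unexpected SAEs from this trial are sent to the participating site when the report is submitted to the MSKCC IRB/PB, with the stamped copy forwarded once received. The existing grade 5 provision can stay.

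The cost is one sentence in the protocol and one e-mail or fax per unexpected SAE to one outside site. The small downside is that the first notice may precede any IRB comment. Section 17.3 does not avoid that for outside reports either. The change does not touch treatment, sample size or analysis.
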